9.5.2 Schedule of Procedures/Assessments Core Study

Table 5 presents the Schedule of Procedures/Assessments for the Core Study.

Table 5 Schedule of Procedures/Assessments in Study E2007-G000-338 (Core Study)

(revised per Amendments 01, 04, and 05)

| Phase | Prerandomization | Randomization | | | | | | | | | |
|---|------------------|---------------------|------------------------|----|----|--------------------------|-----|----------------|----------|--------------------------------|---------------------------------|
| | | Screening/Base line | Titration ^a | | | Maintenance ^b | | | Early DC | Follow-up | |
| Visit | 1 ^a | | 2 ^c | 3 | 4 | 5 | 6 | 7 ^d | | Follow-up, 1 week ^e | Follow-up, 4 weeks ^e |
| Week | (up to -8) | 1 | 2 | 4 | 7 | 13 | 19 | | 20 | 23 | |
| Day | (up to -56) | 1 | 8 | 22 | 43 | 85 | 127 | | 134 | 155 | |
| Procedures/ Assessments | | | | | | | | | | | |
| Informed consent/assent | X | | | | | | | | | | |
| Inclusion/exclusion | X | X ^f | | | | | | | | | |
| Randomization | | X ^f | | | | | | | | | |
| Physical and neurological examination | X | | | | | | | | | | |
| Medical history ^g | X | | | | | | | | | | |
| Prior/concomitant medications | X | X | X | X | X | X | X | X | X | X | X |
| Vital signs, height and weight ^h | X | X | X | X | X | X | X | X | | X | (X) ⁱ |
| ECG | X | | | | | | | | | | (X) ⁱ |
| CCI | | | | | | | | | | | |
| C-SSRS ^k | X | | | | | X | | X | | X | (X) ⁱ |

Table 5 Schedule of Procedures/Assessments in Study E2007-G000-338 (Core Study)

(revised per Amendments 01, 04, and 05)

| Phase | Prerandomization | Randomization | | | | | | | | | |
|--|---------------------|------------------------|---|----|--------------------------|----------------|----------------|----------------|--------------------------------|---------------------------------|------------------|
| Period | Screening/Base line | Titration ^a | | | Maintenance ^b | | | Early DC | Follow-up | | Unscheduled |
| Visit | 1 ^a | 2 ^c | 3 | 4 | 5 | 6 | 7 ^d | | Follow-up, 1 week ^e | Follow-up, 4 weeks ^e | |
| Week | (up to -8) | 1 | 2 | 4 | 7 | 13 | 19 | | 20 | 23 | |
| Day | (up to -56) | 1 | 8 | 22 | 43 | 85 | 127 | | 134 | 155 | |
| Procedures/ Assessments | | | | | | | | | | | |
| Urine pregnancy test ^l | | X | X | X | X | X | X | X | | X | (X) ⁱ |
| Serum pregnancy test ^l | X | | | | | | | | | | |
| Clinical laboratory tests ^m | X | X ⁿ | | X | | | X ⁿ | X ⁿ | | X | (X) ⁱ |
| Viral tests (HBsAg, HepC) | X | | | | | | | | | | |

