| Urine drug testing ^o | X | | | | | | | | | | |
| Dispense/collect seizure diary | X | X | X | X | X | X | X ^p | X | X | X | (X) ⁱ |
| IxRS | X | X | X | X | X | X | X | X | | X | (X) ⁱ |
| Dispense study drug | | X | X | X | X | X | X | | | | (X) ⁱ |
| Administer study | | | | | X ^r | X ^r | | | | | |

Table 5 Schedule of Procedures/Assessments in Study E2007-G000-338 (Core Study)

(revised per Amendments 01, 04, and 05)

| Phase | Prerandomization | Randomization | | | | | | | | | |
|--|---------------------|------------------------|---|----|--------------------------|----------------|----------------|----------------|--------------------------------|---------------------------------|------------------|
| Period | Screening/Base line | Titration ^a | | | Maintenance ^b | | | Early DC | Follow-up | | Unscheduled |
| Visit | 1 ^a | 2 ^c | 3 | 4 | 5 | 6 | 7 ^d | | Follow-up, 1 week ^e | Follow-up, 4 weeks ^e | |
| Week | (up to -8) | 1 | 2 | 4 | 7 | 13 | 19 | | 20 | 23 | |
| Day | (up to -56) | 1 | 8 | 22 | 43 | 85 | 127 | | 134 | 155 | |
| Procedures/ Assessments | | | | | | | | | | | |
| drug at site | | | | | | | | | | | |
| Retrieve unused study drug | | | X | X | X | X | X | X | | | (X) ⁱ |
| Adverse events | X | X | X | X | X | X | X | X | X | X | X |
| CCI | | | | | | | | | | | |
| Perampanel blood concentration samples | | | | | X ^r | X ^r | X ^s | X ^s | X ^s | | (X) ⁱ |
| CGI-S | | X | | | | | | | | | |
| CGI-I | | | | | | | X | X | | | (X) ⁱ |
| Pharmacogenomic blood samples ^t | | X | | | | | | | | | |

Footnotes for Table 5:

AED = antiepileptic drug; CGI-I = Clinical Global Impression of Improvement; CGI-S = Clinical Global Impression of Severity; C-SSRS = Columbia Suicide Severity Rating Scale; DC = discontinuation; ECG = electrocardiogram; EEG = electroencephalogram; CCI [REDACTED] HBsAg = Hepatitis B surface antigen; HepC = Hepatitis C; CCI [REDACTED] PK = pharmacokinetic

- a: Visits will have a window of ± 3 days with at least 10 days between visits (with the exception of Visit 3).
- b: Visits will have a window of ± 6 days.
- c: There must be at least 4 weeks between Visits 1 and 2.
- d: For those subjects who have completed Visit 7 study assessments and who are rolling over into Extension A, Visit 7 will serve as the End-of-Core Study visit and the beginning of the blinded Conversion Period of Extension A. (revised per Amendments 04 and 05)

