8.2.2 Treatment Duration for Safety Analyses

The treatment duration for non-AE safety variables is considered to begin at or after the first dose of study drug on Day 1 and ends 14 days after the last dose of double-blind study medication. For AEs, the treatment duration is considered to begin on Day 1 and ends 28 days after the last dose of double-blind study medication.

The post-treatment duration is considered to begin on the day after the treatment duration for safety. Since it is not always possible for all study participants to come in for their clinic visits on the exact day specified in the protocol schedule, the visit week of a subject's visit will be based on the actual visit occurring during the treatment duration. These visits will be used to create by visit summaries for laboratory, and vital signs data. The end of treatment value is the last non-missing value in the treatment duration.

Any concomitant medication taken within the 14 days after the last dose data will be listed/summarized as part of the concomitant medication listing/table.

AEs for the subject were collected and reported on CRF starting from the time the subject signed informed consent to the last visit in the Treatment Phase following the subject's last dose. Serious AEs were collected for 28 days after the last dose.

For summaries of safety by time points, the time points will be relative to date of first dose. For standardized reporting, study day windows relative to the first dose (Day 1) in the study will be applied to determine into which week the data will be mapped. Scheduled, unscheduled, and early withdrawal visits will be mapped to weeks. [Table 2](#) below gives the mapping of relative day ranges to week for vital sign assessments. [Table 3](#) below gives the mapping of relative day ranges to week for laboratory assessments. If a subject did not have a recorded observation falling within a given range of days in order to be assigned to a week, the subject's data for that week will be regarded as missing for summarization purposes. If there are two or more assessments in the same window then:

- if the window is the baseline assessment, then the latest assessment will be used in the summary tables;
- if the window is the follow-up assessment, then the latest assessment will be used in the summary tables;

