If the window is not the baseline or the follow-up assessment, then the assessment closest to the scheduled assessment will be used in the summary tables. Note that if two assessments are equidistant from the scheduled assessment then the earliest assessment of the two (within the allowable window) will be used. .

Table 1: Mapping of Study Day Ranges to Week for Vital Signs and Weight

Windowing Period	Study Day Range (Relative to First Dose)	Week
Pretreatment	Day $\leq 1^a$	0
Treatment	$2 \leq \text{Day} \leq 20$	2
Treatment	$21 \leq \text{Day} \leq 31$	4
Treatment	$32 \leq \text{Day} \leq 66$	7
Treatment	$67 \leq \text{Day} \leq 104$	12
Treatment	$105 \leq \text{Day} \leq 140$	18
	Day Relative to 14 Days After Last Dose	
Post-Treatment	Day $\leq 999^c$	4

- a: All assessments performed on the same date as the date of first dose were to be performed prior to dosing; results from these assessments will be regarded as Pretreatment values in the analyses.
- b: Measurements must have been taken during the treatment duration, ie, within 14 days of the day of last dose, to be included in analyses as on-treatment assessments.
- c: Measurements must have been taken more than 14 days after the day of last dose to be included in analyses as Post-treatment assessments. Target day is 28 days after last dose or Post-treatment Week 4.

It should be noted that for the post-treatment duration, the study week window is defined relative to the last dose, rather than to the first dose.

Table 3: Mapping of Study Day Ranges to Week for Laboratory Assessments

Windowing Period	Study Day Range (Relative to First Dose)	Week
Pretreatment	Day $\leq 1^a$	0
Treatment	$2 \leq \text{Day} \leq 76$	4
Treatment	$77 \leq \text{Day} \leq 140$	18
	Day Relative to 14 Days After Last Dose	
Post-Treatment	Day $\leq 999^c$	4

- a: All assessments performed on the same date as the date of first dose were to be performed prior to dosing; results from these assessments will be regarded as Pretreatment values in the analyses.
- b: Measurements must have been taken during the treatment duration, ie, within 14 days of the day of last dose, to be included in analyses as on-treatment assessments.
- c: Measurements must have been taken more than 14 days after the day of last dose to be included in analyses as Post-treatment assessments. Target day is 28 days after last dose or Post-treatment Week 4.

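### The SAP vital-sign windows put an on-time Visit 4 on Day 19 or 20 into Week 2, leaving Week 4 empty in the by-week summary

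*SAP*

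**What the plan says.** **Protocol, Table 5 (Section 9.5.2).** The day row reads "Day | (up to -56) | 1 | 8 | 22 | 43 | 85 | 127", so Visits 2 to 7 fall on Days 1, 8, 22, 43, 85 and 127. The row "Vital signs, height and weight" is marked at each of these visits. For titration visits, footnote a says: "Visits will have a window of ± 3 days with at least 10 days between visits (with the exception of Visit 3"). For maintenance visits, footnote b says: "Visits will have a window of ± 6 days".

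**SAP, Section 8.2.2.**
- For summaries by time point, readings are assigned to weeks by day range: "study day windows relative to the first dose (Day 1) in the study will be applied to determine into which week the data will be" (…).
- The table titled "Mapping of Study Day Ranges to Week for Vital Signs and Weight" gives Week 2 = Days 2–20, Week 4 = Days 21–31, Week 7 = Days 32–66, Week 12 = Days 67–104 and Week 18 = Days 105–140. It lists no target day for any week.
- "If a subject did not have a recorded observation falling within a given range of days in order to be assigned to a week", that week is treated as missing.
- If two on-treatment readings share a window, the one nearer its scheduled assessment is used, and the earlier one if they are equally near.
- Unscheduled and early-withdrawal readings are mapped too.
- An earlier paragraph of the section says that a subject's visit week follows the actual visit, and that those visits feed the by-visit laboratory and vital-sign summaries.

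**The concern.** An analysis window should contain every day on which the protocol allows the corresponding visit. Here the Week 2 window runs into the first two days of the Visit 4 allowance. A site that follows the protocol exactly can therefore produce a Visit 4 reading that is tabulated under the wrong week, while the subject's Week 4 cell is empty.

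What is at stake is a planned descriptive safety output: change from baseline in blood pressure, pulse and weight at each post-baseline visit (SAP Section 5.6.4), which is also broken down by age (SAP Section 5.3.4). Visit 4 is the only scheduled vital-sign reading between Day 8 and the start of the Maintenance Period on Day 43. Because the section also contains the actual-visit sentence, two programmers could follow the same SAP and produce different Week 4 rows.

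**Working it through.** **Inputs.** Scheduled days and allowances come from Protocol Table 5 (footnote a, ±3 days, is attached to the Titration header; footnote b, ±6 days, to the Maintenance header). The windows come from SAP Section 8.2.2.

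**Step 1: allowed days against windows.** Allowed days = scheduled day ± allowance.

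| Visit | Scheduled day | Allowed days | SAP window | Allowed days outside it |
|---|---|---|---|---|
| 3 | 8 | 5–11 | Week 2: 2–20 | none |
| 4 | 22 | 19–25 | Week 4: 21–31 | 19 and 20 (both go to Week 2) |
| 5 | 43 | 37–49 | Week 7: 32–66 | none |
| 6 | 85 | 79–91 | Week 12: 67–104 | none |
| 7 | 127 | 121–133 | Week 18: 105–140 | none |

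Only Visit 4 is affected, on 2 of its 7 allowed days.

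**Step 2: does the minimum gap between visits exclude the case?** The protocol requires "days with at least 10 days between visits (with the exception of Visit 3"). The exception concerns the step from Visit 2 to Visit 3, so I apply the 10 days between Visits 3 and 4. Visit 4 on Day 19 needs Visit 3 by Day 9 (Days 5–9, 5 choices). Visit 4 on Day 20 needs Visit 3 by Day 10 (Days 5–10, 6 choices). The case is allowed.

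**Step 3: can another scheduled visit fill Week 4?** An on-time Visit 5 comes on Day 37 at the earliest, and the window closes on Day 31. It cannot. Only an unscheduled or early-withdrawal reading on Days 21–31 would fill it.

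**Step 4: which reading represents Week 2?** This depends on a target day that the SAP table does not give.
- Target Day 8 (Visit 3 in the protocol): Visit 3 is at most 3 days away. Visit 4 is 19 − 8 = 11 or 20 − 8 = 12 days away. Visit 3 is used, and the Visit 4 reading appears nowhere in the by-week table.
- Target Day 14 (an assumption, reading Week 2 as its last day): with Visit 3 on Day 8 and Visit 4 on Day 19, the distances are 6 and 5. Visit 4 is used as the Week 2 value and displaces Visit 3.

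Either way Week 4 is empty.

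**Step 5: comparison with the other boundaries.** Midpoints between scheduled days are (8 + 22)/2 = 15, (22 + 43)/2 = 32.5, (43 + 85)/2 = 64 and (85 + 127)/2 = 106. The SAP boundaries are 20/21, 31/32, 66/67 and 104/105. Only the first is far from its midpoint.

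**Step 6: size.** The documents give no distribution of actual visit days, so the following are assumptions applied to the 142 subjects planned for randomization, with no allowance for dropout before Visit 4.

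| Assumed share of Visit 4s on Days 19–20 | Subjects |
|---|---|
| 5% | 0.05 × 142 ≈ 7 |
| 10% | 0.10 × 142 ≈ 14 |
| 24% | 11/46 × 142 ≈ 34 |
| 29% | 2/7 × 142 ≈ 41 |

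The 24% row takes all Visit 3/Visit 4 day pairs that respect the gap as equally likely: 7 × 7 = 49 pairs, less 3 that break it (10 and 19, 11 and 19, 11 and 20), leaves 46, of which 5 + 6 = 11 are affected. The 29% row spreads Visit 4 evenly over its 7 days and ignores the gap.

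**Step 7: check of the remedy.** For Visit 3 (Days 5–11) and Visit 4 (Days 19–25) to map correctly, Week 2 must end no earlier than Day 11 and no later than Day 18. With Week 2 = Days 2–15 and Week 4 = Days 16–31, no allowed day of any visit is misassigned.

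**The case against.** The strongest objection is that the section itself bases the visit week on the actual visit. On that reading a Visit 4 held on Day 19 stays with Visit 4 and nothing is lost. This stands as a genuine ambiguity. It does not settle the matter, because the same section goes on to set explicit day ranges, includes scheduled visits among the data to be mapped, and defines missingness by those ranges.

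Second, a reader might infer that valid safety data are discarded altogether. The documents do not support that. Clinically notable vital signs are counted over every visit, scheduled or not (SAP Section 5.6.4), so an abnormal Day 19 reading still counts. The last post-baseline and end-of-treatment values do not depend on this boundary. Laboratory data have their own table (Days 2–76 = Week 4). Even within the by-week table, loss of the reading depends on taking Day 8 as the target.

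Third, a reader might infer that about 40 subjects will lose their Week 4 value. That figure needs an even spread of visit days and ignores the 10-day gap. The documents support neither choice.

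Fourth, it is tempting to say that the loss occurs just as the dose rises. Protocol Table 1 plans the same daily dose in Weeks 3 and 4, so the planned dose does not change across Days 19–25.

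Finally, the SAP does not commit itself to midpoints, so Day 15 is one acceptable boundary among several.

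**Conclusion.** The point holds as a narrow defect of the window table. Under the stated day ranges, a protocol-compliant Visit 4 on Day 19 or 20 is labelled Week 2, and Week 4 is missing unless an unscheduled or early-withdrawal reading falls on Days 21–31. This needs no assumption beyond applying the table in preference to the actual-visit sentence, with which it conflicts. That the reading also leaves the by-week table depends on Day 8 being the Week 2 target.

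The consequence is small. It is confined to descriptive by-week summaries of vital signs and weight; no efficacy result or hypothesis test uses these windows. The number of subjects affected cannot be derived from the documents; the range of about 7 to 41 of 142 only illustrates the assumed shares. The correction is desirable, and the trial's conclusions do not depend on it.

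**What to change.** In the vital-sign and weight window table of SAP Section 8.2.2, move the Week 2/Week 4 boundary to any point from 11/12 to 18/19. The midpoint is a natural choice: Week 2 = Days 2–15, Week 4 = Days 16–31. Leave the other windows as they are. Add a target-day column (Days 8, 22, 43, 85 and 127, from Protocol Table 5) so that the rule for two readings in one window has a defined reference. State whether the day ranges or the actual visit determine the week, and amend the sentence that says otherwise.

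The cost is two numbers, one column and one sentence in the SAP, with the matching change in the programming specifications. The protocol, data collection and efficacy analyses are not touched.

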8.2.3 Handling of Replicate Data

A subject having an AE coded to the same preferred term more than once during the study will be counted only once in the incidence calculations for that AE. Similarly, if a subject has more than one AE in a single body system, the incidence will be counted only once for that body system. If a subject has the same AE more than once, the occurrence that is of greatest severity will be used in the calculation of the incidence of individual AE by severity. Similarly, the AE considered most closely related to study drug will be used in the calculation of incidence of individual AE by relationship.

If the subject has taken the same concomitant medication (as coded to preferred WHO-drug term) more than once, the subject will be counted only once in the tabulation.

9 PROGRAMMING SPECIFICATIONS

The rules for programming derivations and dataset specifications are provided in separate documents.

10 STATISTICAL SOFTWARE

All statistical analyses will be performed using SAS.

11 MOCK TABLES, LISTINGS AND GRAPHS

The study table, listing and graph (TLG) shells will be provided in a separate document, which will show the content and format of all tables, listings, and graphs in detail.

12 REFERENCES

Conover, W. J. and Iman, Ronald L. Analysis of Covariance Using the Rank Transformation. *Biometrics*, Vol. 38, No. 3, Special Issue: Analysis of Covariance (Sep., 1982), pp. 715- 724.

Hodges, J. L., Jr. and Lehmann, E. L. (1963). Estimates of location based on rank tests, *The Annals of Math. Statistics*, 34, 598-611.

13 APPENDICES**13.1 Sponsor's Grading for Determining Markedly Abnormal Laboratory Results**

The following table is of Sponsor's Grading for Laboratory Values from the version in the protocol, Appendix 1.

Sponsor's Grading for Laboratory Values				
	Grade 1	Grade 2	Grade 3	Grade 4
BLOOD/BONE MARROW				
Hemoglobin	< LLN – 10.0 g/dL < LLN – 100 g/L < LLN – 6.2 mmol/L	< 10.0 – 8.0 g/dL < 100 – 80 g/L < 6.2 – 4.9 mmol/L	< 8.0 g/dL < 80 g/L < 4.9 mmol/L; transfusion indicated	life-threatening consequences; urgent intervention indicated
Leukocytes (total WBC)	< LLN – $3.0 \times 10^9/L$ < LLN – 3000/mm ³	< $3.0 - 2.0 \times 10^9/L$ < 3000 – 2000/mm ³	< $2.0 - 1.0 \times 10^9/L$ < 2000 – 1000/mm ³	< $1.0 \times 10^9/L$ < 1000/mm ³
Lymphocytes				
• 2-6 years old	NA	NA	NA	NA
• 7-12 years old	NA	NA	NA	NA
• 12 years or older	< LLN – 800/mm ³ < LLN – $0.8 \times 10^9/L$	< 800 – 500/mm ³ < $0.8 - 0.5 \times 10^9/L$	< 500 – 200/mm ³ < $0.5 - 0.2 \times 10^9/L$	< 200/mm ³ < $0.2 \times 10^9/L$
Neutrophils	< LLN – $1.5 \times 10^9/L$ < LLN – 1500/mm ³	< $1.5 - 1.0 \times 10^9/L$ < 1500 – 1000/mm ³	< $1.0 - 0.5 \times 10^9/L$ < 1000 – 500/mm ³	< $0.5 \times 10^9/L$ < 500/mm ³
Platelets	< LLN – $75.0 \times 10^9/L$ < LLN – 75,000/mm ³	< $75.0 - 50.0 \times 10^9/L$ < 75,000 – 50,000/mm ³	< $50.0 - 25.0 \times 10^9/L$ < 50,000 – 25,000/mm ³	< $25.0 \times 10^9/L$ < 25,000/mm ³
METABOLIC/LABORATORY				
Albumin, serum- low (hypoalbuminemia)	< LLN – 3 g/dL < LLN – 30 g/L	< 3 – 2 g/dL < 30 – 20 g/L	< 2 g/dL < 20 g/L	life-threatening consequences; urgent intervention indicated
Alkaline phosphatase	> ULN – $3.0 \times ULN$	> $3.0 - 5.0 \times ULN$	> $5.0 - 20.0 \times ULN$	> $20.0 \times ULN$
ALT, SGPT (serum glutamic pyruvic transaminase)	> ULN – $3.0 \times ULN$	> $3.0 - 5.0 \times ULN$	> $5.0 - 20.0 \times ULN$	> $20.0 \times ULN$
AST, SGOT (serum glutamic oxaloacetic transaminase)	> ULN – $3.0 \times ULN$	> $3.0 - 5.0 \times ULN$	> $5.0 - 20.0 \times ULN$	> $20.0 \times ULN$
Bicarbonate, serum-low	< LLN – 16 mEq/L	< 16 – 11 mEq/L	< 11 – 8 mEq/L	< 8 mEq/L
Bilirubin (hyperbilirubinemia)	> ULN – $1.5 \times ULN$	> $1.5 - 3.0 \times ULN$	> $3.0 - 10.0 \times ULN$	> $10.0 \times ULN$
Calcium, serum-low (hypocalcemia)	< LLN – 8.0 mg/dL < LLN – 2.0 mmol/L	< 8.0 – 7.0 mg/dL < 2.0 – 1.75 mmol/L	< 7.0 – 6.0 mg/dL < 1.75 – 1.5 mmol/L	< 6.0 mg/dL < 1.5 mmol/L
Calcium, serum-high (hypercalcemia)	> ULN – 11.5 mg/dL > ULN – 2.9 mmol/L	> 11.5 – 12.5 mg/dL > 2.9 – 3.1 mmol/L	> 12.5 – 13.5 mg/dL > 3.1 – 3.4 mmol/L	> 13.5 mg/dL > 3.4 mmol/L
Cholesterol, serum-high (hypercholesterolemia)	> ULN – 300 mg/dL > ULN – 7.75 mmol/L	> 300 – 400 mg/dL > 7.75 – 10.34 mmol/L	> 400 – 500 mg/dL > 10.34 – 12.92 mmol/L	> 500 mg/dL > 12.92 mmol/L
Creatinine	> ULN – $1.5 \times ULN$	> $1.5 - 3.0 \times ULN$	> $3.0 - 6.0 \times ULN$	> $6.0 \times ULN$
GGT (γ -Glutamyl transpeptidase)	> ULN – $3.0 \times ULN$	> $3.0 - 5.0 \times ULN$	> $5.0 - 20.0 \times ULN$	> $20.0 \times ULN$
Glucose, serum-high (hyperglycemia)	Fasting glucose value: > ULN – 160 mg/dL > ULN – 8.9 mmol/L	Fasting glucose value: > 160 – 250 mg/dL > 8.9 – 13.9 mmol/L	> 250 – 500 mg/dL; > 13.9 – 27.8 mmol/L; hospitalization indicated	> 500 mg/dL; > 27.8 mmol/L; life-threatening consequences

Sponsor's Grading for Laboratory Values				
	Grade 1	Grade 2	Grade 3	Grade 4
Glucose, serum-low (hypoglycemia)	< LLN – 55 mg/dL < LLN – 3.0 mmol/L	< 55 – 40 mg/dL < 3.0 – 2.2 mmol/L	< 40 – 30 mg/dL < 2.2 – 1.7 mmol/L	< 30 mg/dL < 1.7 mmol/L life-threatening consequences
Phosphate, serum-low (hypophosphatemia)	<LLN- 2.5 mg/dL <LLN – 0.8 mmol/L	<2.5-2.0 mg/dL <0.8-0.6 mmol/L	<2.0-1.0 mg/dL <0.6-0.3 mmol/L	< 1.0 mg/dL < 0.3 mmol/L life-threatening consequences
Potassium, serum-high (hyperkalemia)	> ULN – 5.5 mmol/L	> 5.5 – 6.0 mmol/L	> 6.0 – 7.0 mmol/L; hospitalization indicated	> 7.0 mmol/L life-threatening consequences
Potassium, serum-low (hypokalemia)	< LLN – 3.0 mmol/L	< LLN – 3.0 mmol/L; symptomatic intervention indicated	< 3.0 – 2.5 mmol/L; hospitalization indicated	< 2.5 mmol/L life-threatening consequences
Sodium, serum-high (hypernatremia)	> ULN – 150 mmol/L	> 150 – 155 mmol/L	> 155 – 160 mmol/L; hospitalization indicated	> 160 mmol/L; life-threatening consequences
Sodium, serum-low (hyponatremia)	< LLN – 130 mmol/L	NA	< 130 – 120 mmol/L	< 120 mmol/L; life-threatening consequences
